- After a grade 3 or higher non-hematological toxicity (despite optimal supportive care) resolves, ibrutinib will be restarted as follows;

Occurrence	Action
1 st	Hold ibrutinib until recovery to Grade \leq 1 or baseline; restart at the original dose level (420mg daily).
2 nd	Hold ibrutinib until recovery to Grade \leq 1 or baseline; restart at one dose level lower (280mg daily).
3 rd	Hold ibrutinib until recovery to Grade \leq 1 or baseline; restart at one dose level lower (140mg daily).
4 th	Discontinue ibrutinib.

- A high number of circulating malignant cells ($>400,000/\mu\text{L}$) may confer increased risk; these subjects should be closely monitored. Administer supportive care such as hydration and/or leukapheresis as indicated. Ibrutinib may be temporarily held, and PI should be contacted.
- In the event that ibrutinib is withheld for a toxicity of 28 consecutive days the study drug should be discontinued. However, if clinical benefit outweighs the risk of restarting treatment then patient may restart study drug after > 28 consecutive days off study drug per PI discretion.
- For fludarabine, after a grade 3 non-hematological toxicity (despite optimal supportive care), when the toxicity resolves to grade 2 or lower and clinical benefit outweighs the risk, treatment can be restarted with 20% dose reduction on the subsequent cycle. Patients experiencing \leq Grade 2 side effects may continue treatment. Supportive measures as appropriate should be taken to minimize side effects. An interruption of study drug administration is permissible. In select cases where a subject has uncomfortable grade 2 toxicities, dose may be reduced by one dose level per PI discretion.

Dose changes must be recorded in the Dose Administration eCRF.

5.4.4 Dose modification for hepatic impaired subjects:

- Ibrutinib is metabolized in the liver and therefore subjects with clinically significant hepatic impairment at the time of screening (Child- Pugh class B or C) are excluded from study participation.
- For subjects with existing chronic mild hepatic impairment (Child-Pugh class A) at enrollment, the starting dose has to be adjusted to a level of 280 mg daily (two capsules).
- For subjects who develop mild liver impairment while on study (Child-Pugh class A), the recommended dose reduction for ibrutinib is to a level of 280 mg daily (two capsules).

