- For subjects who develop moderate liver impairment while on study (Child-Pugh class B), the recommended dose reduction is to a level of 140 mg daily (one capsule).
- Subjects who develop severe hepatic impairment (Child-Pugh class C) must hold study drug until resolved to moderate impairment (Child-Pugh class B) or better.
- Subjects who develop acute hepatic toxicity with liver enzymes Grade 3 or higher while on study should be managed per standard dose modification guidelines in Section 5.4.3.

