5.5 Holding of Study Drug Administration

5.5.1 Ibrutinib and Surgical Procedures:

Consider the benefit-risk of withholding ibrutinib for at least 3 to 7 days pre and post-surgery depending upon the type of surgery and the risk of bleeding.

5.5.2 Medically Necessary Conditions to Hold Study Drugs:

- If medically necessary reasons to hold ibrutinib occur during treatment (i.e. concurrent infection, impending workups for diagnostic and/or therapeutic purposes), ibrutinib can be held based on the study team's discretion.
- If medically necessary reasons to hold fludarabine occur during treatment (i.e. concurrent infection, emergence of autoimmune cytopenia, impending workups for diagnostic and/or therapeutic purposes), fludarabine can be delayed up to 2 cycles while continuing ibrutinib until the medical reasons to hold fludarabine resolve or return to baseline. If fludarabine is delayed beyond 2 cycles, fludarabine will be omitted and the patient will continue treatment with ibrutinib only.
- Supportive medications including allopurinol, and acyclovir (if indicated) intended to start at cycle 3 will be delayed until fludarabine starts or not given if fludarabine is omitted. Weekly labs intended for cycles 3 and 4 will be delayed until fludarabine starts or not performed if fludarabine is omitted.

5.5.3 Permanent discontinuation of study drug administration in case of treatment related adverse events:

- Serious or life threatening cardiac arrhythmias (grade 3 or 4)
- Severe infection (requiring vasopressor support > 24h, or intubation)
- Any grade 4 toxicity excluding readily reversible metabolic or laboratory abnormalities or hematologic toxicities
- Progressive disease as defined in section 7.3
- Pregnancy or unwillingness to use acceptable method of contraception

Patients who will not be able to receive further study drug administration will be followed for safety and after resolution of the event will continue to be followed at regular intervals and will undergo reassessment of disease as outlined in section 6 and 7.

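### The ibrutinib restart rule in 5.4.3 has no exception for the permanent stops in 5.5.3, and the fludarabine cytopenia table in 5.4.1 has one gap and two overlaps

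*Combined protocol and SAP*

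**What the plan says.** **Ibrutinib.** Section 5.4.3 states: "After a grade 3 or higher non-hematological toxicity (despite optimal supportive care) resolves, ibrutinib will be restarted as follows". Its table gives 420 mg after the first occurrence, 280 mg after the second and 140 mg after the third, and stops the drug at the fourth. The fludarabine rule in the same section is narrower: "For fludarabine, after a grade 3 non-hematological toxicity (despite optimal supportive care), when the toxicity resolves to grade 2 or lower".

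Section 5.5.3 lists the treatment-related events that end study drug permanently. Three are toxicities: grade 3-4 serious or life-threatening arrhythmia; infection needing vasopressors for more than 24 hours or intubation; and "Any grade 4 toxicity excluding readily reversible metabolic or laboratory abnormalities or hematologic toxicities". The list also holds progressive disease and "Pregnancy or unwillingness to use acceptable method of contraception", which are not toxicities and play no part here.

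Three other sections bear on restart or discontinuation. Section 5.4.2 leaves restart after new-onset atrial fibrillation to the principal investigator and a consulting physician, without a grade limit. Section 9.7 says that drug is stopped for adverse events as set out in 5.5. The arrhythmia paragraph of 11.2.1 refers the reader to 5.4 only.

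**Fludarabine.** In the 5.4.1 table the upper count row is ANC 750 to <1,000 or platelets 50,000 to <75,000, resuming at the original dose. The lower row is ANC <500 or platelets <50,000, resuming at a 20% reduced dose. Both rows defer, check counts weekly, use the same recovery thresholds and omit fludarabine after 8 weeks without recovery. A footnote waives delay and reduction when the cytopenia is considered due to CLL.

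**The concern.** A clinician whose patient recovers from intubation for a treatment-related infection, from a grade 3 arrhythmia, or from a non-exempt grade 4 toxicity finds one section telling them to resume ibrutinib at full dose and another telling them never to resume it. According to section 10.0, this is the first trial to combine these two drugs, so the rechallenge decision should not depend on which page is open.

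The fludarabine table leaves a similar difficulty. At ANC 600 with platelets 100,000 it gives no instruction, although both a higher ANC (750 to <1,000) and a lower one (<500) lead to deferral.

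There is also a possible link to the endpoints. The primary safety endpoint in 9.1 counts discontinuations for intolerable side effects, with decision limits in 9.3 at 3 of 13 and 4 of 27. Under 9.3 an early stop for drug-related toxicity also counts as non-response. The section that is followed can therefore decide whether a countable event occurs.

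**Working it through.** **Step 1: the ibrutinib rules side by side, for a first treatment-related event that resolves.**

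| Event | 5.4.3 | 5.5.3 |
|---|---|---|
| Non-hematologic grade 3, not on the 5.5.3 list | restart at 420 mg | silent |
| Grade 4 metabolic or laboratory abnormality, readily reversible | restart at 420 mg | exempt |
| Other non-hematologic grade 4 | restart at 420 mg | permanent stop |
| Serious or life-threatening arrhythmia, grade 3-4 | restart at 420 mg | permanent stop |
| Infection with vasopressors >24 h or intubation (grade 3 or higher) | restart at 420 mg | permanent stop |

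The first two lines are consistent. The last three are not. Scope does not separate the sections: the headings of both 5.4 and 5.5.3 are limited to treatment-related toxicity or events. The same conflict holds at the second and third occurrences and disappears at the fourth, where both sections stop the drug.

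**Step 2: the fludarabine table.** Crossing four ANC bands with three platelet bands gives 4 × 3 = 12 combinations. U is the upper row (original dose) and L the lower row (20% reduced).

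| ANC per µL | PLT ≥75,000 | PLT 50,000 to <75,000 | PLT <50,000 |
|---|---|---|---|
| ≥1,000 | none (full dose intended) | U | L |
| 750 to <1,000 | U | U | **U and L** |
| 500 to 749 | **none (gap)** | U | L |
| <500 | L | **U and L** | L |

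One combination is silent, two carry two resumption doses, and 12 − 1 − 2 = 9 are clear. The separate row for hemoglobin below 11 g/dL with autoimmune hemolysis omits fludarabine and does not fill the gap.

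**Step 3: the plan's own design figures for the safety endpoint.** Inputs from 9.3: 13 subjects in stage 1, continue with 2 or fewer discontinuations; 27 in total, reject the null with 4 or fewer; null rate 30%, alternative 10%.

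P(reject) = Σ over x = 0, 1, 2 of P(Bin(13, p) = x) × P(Bin(14, p) ≤ 4 − x)

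- At p = 0.10: 0.2542 × 0.9908 + 0.3672 × 0.9559 + 0.2448 × 0.8416 = 0.809, against a stated 81%.
- At p = 0.30: 0.047, against a stated 0.05.

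Both figures reproduce. They are functions of the true discontinuation rate and do not depend on which section is followed. What could change is the rate itself, and the documents do not say how often 5.5.3 events are expected in six cycles or how sites would handle them.

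**Step 4: the repaired table.** Let the upper row begin at ANC 500 and let the lower row prevail when both match. The result is 6 combinations at 20% reduced, 5 at original dose and 1 at full dose without deferral: 6 + 5 + 1 = 12, each with one action. Only the three defective combinations change. ANC 500 to 749 with PLT <50,000 would now match both rows, but precedence keeps it at 20% reduced.

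**The case against.** The strongest reply is that the two sections fit together. Section 5.5.3 is the specific rule, with named events, and 9.7 repeats that drug is stopped as 5.5 sets out. The severe-infection and grade 4 criteria reappear in 9.5 as study-stopping events, which suggests a deliberate higher tier. The words grade 3 or higher in 5.4.3 also have a use, because exempt grade 4 laboratory events need a restart rule. Most of this stands, and a reader who infers that the protocol leaves precedence wholly open goes too far. What remains is that the harmony must be inferred. Nothing in 5.4.3 takes out a grade 3 arrhythmia or a severe infection.

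Some supporting citations are weak. Section 5.4.4 says of acute hepatic toxicity that "liver enzymes Grade 3 or higher while on study should be managed per standard dose modification guidelines in Section 5.4.3", but these are laboratory abnormalities and largely fall under the 5.5.3 exemption. The 11.2.1 note concerns arrhythmia that persists and asks for a weighing of risk and benefit. Section 5.4.2 permits a restart but does not direct one.

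On the fludarabine table, it is fair that the overlaps differ only by a 20% dose reduction and that deferral in the gap follows from its neighbours. The resumption dose is still undefined in the gap and contradictory in the overlaps.

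Section 9.5 gives partial cover: probably or definitely related severe infections and non-exempt grade 4 toxicities are monitored whether or not drug is restarted. It does not list grade 3 arrhythmia, and it does not tell the clinician whether to restart.

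**Conclusion.** The point holds as a wording defect with a patient-safety consequence. Three kinds of treatment-related event literally meet a restart rule and a permanent-stop rule; 5.5.3 is very probably meant to prevail, but 5.4.3 does not say so. In the fludarabine table, 3 of 12 combinations are defective (1 silent, 2 contradictory), for cytopenia not considered due to CLL.

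A reader might infer that the primary safety analysis is compromised. The documents do not support that. Power and type I error reproduce, and a shift in the discontinuation count is possible but depends on an event frequency and site behaviour that are not given.

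A reader might also infer that the fludarabine table feeds the safety endpoint, or that 9.1 must be redefined. Section 5.5.2 says of a prolonged fludarabine hold that "fludarabine will be omitted and the patient will continue treatment with ibrutinib only". The protocol thus treats omission as distinct from stopping treatment, and no change to 9.1 is needed on this account.

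**What to change.** 1. Add to 5.4.2 and 5.4.3: 'except for the toxicity events listed in 5.5.3, which require permanent discontinuation'. Section 5.4.4 inherits this through its reference to 5.4.3.
2. In the arrhythmia paragraph of 11.2.1, cite 5.5.3 as well as 5.4.
3. In the fludarabine table, set the upper row to ANC 500 to <1,000/µL or PLT 50,000 to <75,000/µL, and state that the more severe row applies when both match.

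Starting the upper row at 500 keeps the protocol's own severe cut-off of ANC <500, which is used for fludarabine and ibrutinib in 5.4.1 and for growth factors in 5.6.2. Raising the lower row to ANC <750 would also close the gap, but it would change a combination that is already clear (ANC 500 to 749 with PLT 50,000 to <75,000) from original to reduced dose.

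The cost is amendment text only, with no new data and no change to sample size or decision rules. Expect slightly more fludarabine reductions in the two overlap combinations, and possibly a slightly less favourable discontinuation count if ibrutinib would otherwise have been restarted after 5.5.3 events.

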5.6 Supportive Care (non-investigational)

5.6.1 Blood Products: Patients will be transfused packed red blood cells and platelets as clinically indicated. All required blood products will be irradiated prior to transfusion.

5.6.2 Growth Factors: Filgrastim or peg-filgrastim may be used to accelerate count if ANC < 500/uL at the PI's discretion, for example, for febrile neutropenia.

5.6.3 Anti-infective agents will be used as indicated for treatment of intercurrent infections.

5.6.4 PCP prophylaxis: Sulfamethoxazole/trimethoprim DS PO once daily 3 times per week (or alternative agent in case of sulfa allergy) from cycle 1 to 9 and beyond, at the discretion of the PI. Patients who may be at an increased risk of PCP infection include those who are taking long-term

high-dose steroids or immune suppressants, and those who had prior PCP infection. Patients allergic to sulfa drugs who are deemed appropriate for prophylaxis may be given an alternative agent at the discretion of the PI.

5.6.5 Anti-viral prophylaxis: Acyclovir 800 mg PO twice daily or valacyclovir 500mg PO once daily may be used the discretion of the PI (not obligatory).

5.7 Permitted and Non Permitted Concomitant Medications (Investigators Brochure)

Patients may continue most medications they were prescribed prior to study enrollment for co-morbid conditions. No formal drug-drug interaction studies have been conducted therefore we ask patients to report all medications and over the counter drugs they are taking so we can monitor for any drug-drug interactions. Treatment for autoimmune cytopenias is permitted only during cycles with ibrutinib alone, but not during cycle 3 and 4 when fludarabine is added. Treatment for autoimmune cytopenias should not exceed 14 days at doses that do not exceed 100mg per day of prednisone or equivalent.

5.7.1 Guideline for Use of CYP Inhibiting Drugs

Ibrutinib is metabolized primarily by CYP3A. Avoid co-administration with strong CYP3A or moderate CYP3A inhibitors and consider alternative agents with less CYP3A inhibition.

- If a strong CYP3A inhibitor (eg, ketoconazole, indinavir, nelfinavir, ritonavir, saquinavir, clarithromycin, telithromycin, itraconazole, nefazadone, posaconazole, or cobicistat) must be used, reduce ibrutinib dose to 140 mg or withhold treatment temporarily (for 7 days or less). Subjects should be monitored for signs of ibrutinib toxicity.
- If a moderate CYP3A inhibitor (eg, voriconazole, erythromycin, amprenavir, aprepitant, atazanavir, ciprofloxacin, crizotinib, darunavir/ritonavir, diltiazem, fluconazole, fosamprenavir, imatinib, verapamil, amiodarone, or dronedarone) must be used, reduce ibrutinib to 140 mg (for 840 mg/day dose, reduce to 280 mg) for the duration of the inhibitor use. Avoid grapefruit and Seville oranges during ibrutinib treatment, as these contain moderate inhibitors of CYP3A.
- No dose adjustment is required in combination with mild inhibitors.
- Avoid concomitant use of strong CYP3A inducers (eg, carbamazepine, rifampin, phenytoin, and St. John's Wort). Consider alternative agents with less CYP3A induction.
- A list of common CYP3A inhibitors and inducers is provided in Appendix 3 of the IB. A comprehensive list of inhibitors, inducers, and substrates may be found at <http://medicine.iupui.edu/clinpharm/ddis/main-table/>. This website is continually revised and should be checked frequently for updates.
- For the most comprehensive effect of CYP3A inhibitors or inducers on ibrutinib exposure, please refer to the current version of the IB.

5.7.2 Concomitant Use of QT Prolonging Agents

Any medications known to cause QT prolongation should be used with caution; periodic ECG and electrolyte monitoring should be considered.

5.7.3 Concomitant Use of Antiplatelet Agents and Anticoagulants

Use ibrutinib with caution in subjects requiring anticoagulants or medications that inhibit platelet function. In an in vitro platelet function study, inhibitory effects of ibrutinib on collagen induced platelet aggregation were observed. Supplements such as fish oil and vitamin E preparations should be avoided during treatment with ibrutinib. Bleeding events of any grade, including bruising and petechiae, occurred in subjects treated with ibrutinib. Subjects with congenital bleeding diathesis have not been studied. Ibrutinib should be held at least 3 to 7 days pre- and post-surgery depending upon the type of surgery and the risk of bleeding. For guidance on ibrutinib and the use of anticoagulants during procedures/surgeries see Section 5.5.

Subjects requiring the initiation of therapeutic anticoagulation therapy (eg, atrial fibrillation) should be observed closely for signs and symptoms of bleeding and the risks and benefits of continuing ibrutinib treatment should be considered.

5.8 Special instructions for patients

5.8.1 Immunizations: Live vaccines are contraindicated in this patient population. Subjects who would like to receive other routine non-attenuated vaccinations will be allowed to do so. Patients will be advised not to receive live viral vaccines. The ability to generate an immune response to any vaccine following administration of ibrutinib has not been studied.

5.8.2 Birth control: Subjects with reproductive potential who are sexually active must use acceptable methods of contraception during the study and for 90 days after the last dose of ibrutinib. Examples of acceptable methods of contraception include condoms, implants, injectables, combined oral contraceptives, intrauterine devices, true sexual abstinence, or sterilized partner. Note that that periodic abstinence, e.g., calendar, ovulation, symptothermal, post-ovulation methods or withdrawal, are not acceptable methods of contraception.

5.9 Prohibited Concomitant Medications

- Any chemotherapy, anticancer immunotherapy, experimental therapy, or radiotherapy are prohibited while the subject is receiving ibrutinib treatment.
- For patients who were newly diagnosed with a second malignancy, the study drug can be interrupted while the patient undergoes further evaluation and treatment with definitive, time-limited anti-cancer therapy (i.e. localized breast cancer requiring surgery and adjuvant chemoradiation). If the second malignancy requires long-term therapy (> 6 months) or a definite therapy is not available (i.e. metastatic solid tumor), the patient will be taken off study.
- Corticosteroids for the treatment of the underlying disease is prohibited. Corticosteroids for the treatment of non-cancer related reasons for longer than 14 consecutive days at doses >20mg/day of prednisone or equivalent, or at doses >100mg of prednisone or its equivalent at any time point is prohibited.

6.0 CLINICAL MONITORING

Samples will be ordered and tracked through the CRIS screens. Should a CRIS screen not be available, the NIH form 2803-1 will be completed and will accompany the specimen and be filed in the medical record.

Results from other NIH protocols may be used as a part of the study evaluation. Selected results performed from outside institutions are accepted, which are viral studies, flow cytometry, CT of neck/chest/abdomen/pelvis, and FISH.

6.1 Study Evaluations: Screening and Baseline (see schedule of events Appendix A)

Screening:

Screening evaluation will include the following (also see schedule of events).

- Complete medical history: relevant past medical history includes medical diagnoses and/or conditions; 1) that are currently ongoing, OR 2) occurred within 1 year of study enrollment, OR 3) occurred before 1 year of study enrollment and were potentially associated with major organ function or with long-term sequelae (i.e. hypertension, hyperlipidemia, diabetes, surgery of major organ system, any malignancy).
- ECOG performance evaluation
- Physical exam will be performed, and subjects will be monitored clinically for atrial fibrillation
- Concomitant medication review

- Complete blood count (CBC) with differential
- Acute Care Panel (includes Na, K, Cl, CO₂, Creatinine, Glucose, and Urea Nitrogen)
- Mineral Panel (Phosphorus, Magnesium, Albumin, and Calcium)
- Total Protein, CK, Uric Acid, and LDH
- Hepatic Panel (includes Alkaline Phosphatase, ALT, AST, Total Bilirubin, and Direct Bilirubin)
- Reticulocyte count
- Coagulation panel (includes PT, PTT)
- Beta-2 microglobulin (B2M)
- Haptoglobin
- Direct antiglobulin test (DAT)
- Iron Studies (includes ferritin, transferrin, iron)
- Folate, Vitamin B12
- Viral serologies for hepatitis B and C, HIV 1/2. For individuals with a positive hepatitis B core antibody, HBV DNA PCR will be performed to screen for subclinical infection within 12 months preceding the start of study drug.
- For females of childbearing potential, one negative pregnancy tests sensitive to 50 mIU within 2 weeks prior to starting study drug
- Flow cytometry panel for CLL (may be done on blood and/or bone marrow and/or lymph node) or immunohistochemistry of lymph node or bone marrow demonstrating CLL/SLL within 3 months prior to starting study drug
- CT of the neck, chest, abdomen and pelvis within 3 months prior to starting study drug. IV and PO contrast will be used unless the patient has a contrast allergy or impaired renal function.
- EKG within 3 months prior to starting study drug

Baseline (day -28 to day 0):

Baseline evaluation will include the following (also see schedule of events).

- Complete medical history: relevant past medical history includes medical diagnoses and/or conditions; 1) that are currently ongoing, OR 2) occurred within 1 year of study enrollment, OR 3) occurred before 1 year of study enrollment and were potentially associated with major organ function or with long-term sequelae (i.e. hypertension, hyperlipidemia, diabetes, surgery of major organ system, any malignancy).
- ECOG performance evaluation
- Physical exam will be performed, and subjects will be monitored clinically for atrial fibrillation
- Concomitant medication review
- HLA typing (if clinically indicated)
- CBC with differential
- Acute Care Panel (Na, K, Cl, CO₂, Creatinine, Glucose, and Urea Nitrogen)
- Mineral Panel (Phosphorus, Magnesium, Albumin, and Calcium)
- Total Protein, CK, Uric Acid, and LDH
- Hepatic Panel (Alkaline Phosphatase, ALT, AST, Total Bilirubin, and Direct Bilirubin)
- Reticulocyte count
- Coagulation panel (PT, PTT)
- Serum protein electrophoresis with immunofixation (SPEP)
- Serum free light chains, quantitative immunoglobulins
- C-reactive protein (CRP)
- Beta-2 microglobulin (B2M)
- Haptoglobin
- Direct antiglobulin test (DAT)
- For females of childbearing potential, pregnancy test
- Lymphocyte phenotyping (T, B, NK)
- IGHV mutation analysis (as this test does not change with time, any prior report is acceptable)

- Flow cytometry panel (optional)
- Bone marrow aspirate and biopsy within 3 months of starting treatment
- Peripheral blood interphase FISH within 3 months prior to starting study drug. FISH panel contains probes for *ATM* (11q22.3), *DI2Z3* (12 cen), *DI3S319* (13q14.3), *LAMPI* (13q34) and *TP53* (17p13.1).
- Lymph node biopsy for research if the patient is willing and has an accessible lymph node (optional)
- Lymphapheresis for research (optional)
- Research blood (up to 80ml)

